#### 6.1.2. Definitions and Conventions

**Study drug** refers to abemaciclib or placebo.

**Study treatment** refers to study drug plus NSAID/fulvestrant.

The **date of randomization** is the date the patient was randomly assigned to study treatment using the interactive web response system (IWRS).

The **date of first dose** is the date of the first dose of study drug or NSAID/fulvestrant.

The **baseline value of a safety assessment** is the last value observed prior to the first dose of study drug or NSAI/fulvestrant.

The **baseline value of an efficacy assessment** is the last value observed prior to the date of randomization. If a patient's first assessment occurs after randomization but prior to the first dose, this assessment will be used as the baseline.

The **study day of a safety event or assessment** will be calculated as:

- the difference between the date of the event or assessment and the date of first dose plus 1 for all events or assessments occurring on or after the day of first dose. For example, if an event occurs on 08JUN2014 and the date of first dose was 06JUN2014, the study day of the event is 3.
- the difference between the date of the event or assessment and the date of first dose for all events or assessments occurring before the day of first dose. For example, if an event occurs on 05JUN2014 and the date of first dose was 06JUN2014, the study day of the event is -1.

The **study day of an efficacy event or assessment** will be calculated as:

- the difference between the date of the event or assessment and the date of randomization plus 1 for all events or assessments occurring on or after the date of randomization.
- the difference between the date of the event or assessment and the date of randomization for all events or assessments occurring before the date of randomization.

One **month** is defined as 365/12 days.

Unless otherwise noted, **summaries of continuous variables** will include a mean, median, standard deviation, minimum, and maximum.

Unless otherwise noted, **summaries of categorical variables** will include the frequency and percentage (relative to the population being analyzed) of each category.

## 6.2. Handling of Dropouts or Missing Data

With the exception of dates, missing data will not be imputed. The method of imputation for any dates that are imputed is described in the relevant section.

## 6.3. Patient Disposition

A detailed description of patient disposition will be provided. It will include a summary of the number and percentage of patients entered into the study, enrolled in the study, treated in the study, reasons for discontinuation from study treatment, and reasons for discontinuation from study. Reason for discontinuation from both study treatment and the study will be summarized by pre-determined categories. If the reason for discontinuation is adverse event (AE), the associated AE term will be reported.

## 6.4. Patient Characteristics

### 6.4.1. Demographics and Performance Status

Patient demographics will be summarized. Patient demographics will include the following:

- race
- age
- country
- height
- weight
- body mass index (BMI)
- baseline Eastern Cooperative Oncology Group (ECOG) performance status (PS).

### 6.4.2. Baseline Disease Characteristics

Disease characteristics will be summarized. Disease characteristics will include the following:

- Initial pathological diagnosis
- Study entry disease status (de novo metastatic disease vs. metastatic recurrent disease vs. locoregionally recurrent disease) for Cohort A
- Prior (neo)adjuvant endocrine therapy (aromatase inhibitor vs. other vs none)
- Prior (neo)adjuvant chemotherapy (yes or no) for Cohort B
- Prior metastatic endocrine therapy (aromatase inhibitor vs. antiestrogen vs. other vs. none) for Cohort B
- Disease-free interval (DFI)
- Treatment-free interval (TFI) for Cohort A
- Sensitivity to endocrine therapy (primary resistance vs. secondary resistance) for Cohort B
- Nature of disease (visceral metastases vs. non-visceral metastases )
- Measurable vs non-measurable disease
- Number of organs involved (1, 2, or 3+)
- Metastatic site
- Estrogen receptor status
- Progesterone receptor status.

Prior (neo)adjuvant endocrine therapy categories will be reported directly from the ‘Prior (neo)adjuvant endocrine therapy’ electronic case report form (eCRF). Prior metastatic endocrine therapy categories will be reported directly from the ‘Prior metastatic endocrine therapy’ eCRF.

Prior (neo)adjuvant chemotherapy will be reported based on data reported on the ‘Systemic Therapy: Prior for this Cancer’ eCRF.

Disease-free interval (DFI) is defined as the period of time between the completion of adjuvant endocrine therapy and disease recurrence for those patients who received adjuvant endocrine therapy. The categories (e.g. relapsed on or within 1 year vs. more than 1 year from completion of adjuvant endocrine therapy) will be reported directly from the ‘Breast Cancer Characteristics

A\_2' eCRF for Cohort A, and 'Breast Cancer Characteristics - B' eCRF for Cohort B, respectively.

Treatment-free interval (TFI) is defined as the period of time between the end date of adjuvant endocrine therapy and the date of informed consent for those patients who received adjuvant endocrine therapy. It will be calculated as the informed consent date – end date of therapy + 1, based on data reported on the 'Disposition: Study Informed Consent' and 'Systemic Therapy: Prior for this Cancer' eCRFs. If only the month and year of a treatment end date is available, the day will be imputed to the 15th. The categories (de novo metastatic vs. <36 months vs. ≥ 36 months vs. recurrent with no adjuvant endocrine) will be derived and reported.

Nature of disease, disease measurability, metastatic site will be reported directly from the 'Nature of Disease' eCRF. The number of organs involved will be derived from the metastatic sites.

### **6.4.3. Historical Illnesses**

Historical illnesses are clinically relevant events in the past that ended before the screening visit. Historical illnesses (using Preferred Term(s) [PTs] from the most current version of the Medical Dictionary for Regulatory Activities [MedDRA]) will be summarized.

### **6.4.4. Prior Therapies**

Prior radiotherapy, surgery, and systemic therapy will be summarized. Prior radiotherapy and surgery will be categorized by reason for regimen. Prior systemic therapies will be categorized by reason for regimen and specific therapy. Frequency of each specific therapy will be tabulated within each reason for therapy.

For cohort B, most recent systemic therapy and the duration of that therapy will be summarized within each of the following subgroups:

- Patients whose most recent systemic therapy was an adjuvant therapy
- Patients whose most recent systemic therapy was for locally advanced or metastatic disease.

This summary will include median duration of treatment (date of end of therapy – date of start of therapy + 1), median time to progression (date of progression – date of first dose + 1), and frequency of each specific therapy. If only the month and year of a treatment date or progression date is available, the day will be imputed to the 15th.

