- relapsed with radiologic evidence of progression while receiving neoadjuvant or adjuvant letrozole or anastrozole, with no subsequent endocrine therapy received following progression

OR

- relapsed with radiologic evidence of progression within 1 year from completion of adjuvant letrozole or anastrozole, with no subsequent endocrine therapy received following progression

OR

- relapsed with radiologic evidence of progression more than 1 year from completion of adjuvant endocrine therapy and then subsequently relapsed with radiologic evidence of progression after receiving treatment with either an antiestrogen or an aromatase inhibitor as first-line endocrine therapy for metastatic disease. Patients may not have received more than 1 line of endocrine therapy or any prior chemotherapy for metastatic disease

OR

- presented de novo with metastatic disease and then relapsed with radiologic evidence of progression after receiving treatment with either an antiestrogen or an aromatase inhibitor as first-line endocrine therapy for metastatic disease. Patients may not have received more than 1 line of endocrine therapy or any prior chemotherapy for metastatic disease.
- [3] have postmenopausal status defined as meeting at least 1 of the following:
- prior bilateral oophorectomy
  - age  $\geq 60$  years
  - age  $< 60$  years and amenorrheic for at least 12 months (in the absence of chemotherapy, tamoxifen, toremifene, or ovarian suppression) and follicle-stimulating hormone (FSH) and estradiol levels in the postmenopausal range
- [4] have 1 of the following, as defined by the Response Evaluation Criteria in Solid Tumors (RECIST) v1.1 (Eisenhauer et al. 2009; see [Attachment 5](#)):
- Measurable disease
  - Nonmeasurable bone-only disease. Nonmeasurable bone-only disease may include any of the following: blastic bone lesions, lytic bone lesions without a measurable soft tissue component, or mixed lytic-blastic bone lesions without a measurable soft tissue component.
- [5] have a performance status (PS) of  $\leq 1$  on the Eastern Cooperative Oncology (ECOG) scale (see [Attachment 4](#))
- [6] have adequate organ function, including:

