Patients in Cohort B will be randomized using the following stratification factors: nature of disease (visceral metastases vs. non-visceral metastases) and sensitivity to endocrine therapy (primary resistance vs. secondary resistance). The presence of visceral metastases refers to lung, liver, pleural, or peritoneal, or adrenal gland involvement at the time of randomization. Primary clinical resistance to endocrine therapy is defined as follows: 1) for endocrine therapy in the adjuvant setting, recurrence within the first 2 years of adjuvant endocrine therapy while on endocrine therapy, or 2) for endocrine therapy in the locoregionally recurrent or metastatic setting, progression within first 6 months of initiating first-line endocrine therapy while on endocrine therapy. Patients receiving prior endocrine therapy who do not meet the definition of primary clinical resistance will be considered to have secondary clinical resistance.

The primary analysis of the PFS endpoint will occur after approximately 170 PFS events have been observed in Cohort A. An interim analysis will be conducted after approximately 119 PFS events are observed to provide early efficacy information and allow for potential early communication with regulatory agencies (see Protocol Section 12.2.6 for details).

The interim analysis of Cohort B will follow the timeline of Cohort A, which will occur only if the interim of Cohort A turns out to be positive. If patients in Cohort A continue being followed for PFS until final analysis, the final analysis of Cohort B will be conducted at the same time of Cohort A final analysis. If Cohort A stops early at interim due to efficacy, the final analysis of Cohort B may be conducted after approximately 105 PFS events have been observed in Cohort B. (see Protocol Section 12.2.14 for details).

For each cohort, all patients will be followed for progression and survival information until death or study completion, whichever occurs first.

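### For Cohort B, SAP 6.4.4 counts time to progression on prior therapy from a term the SAP defines as first dosing on study, so this descriptive summary would generally show values at or below zero

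*SAP*

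**What the plan says.** SAP 6.4.4 introduces an extra table for the second cohort: "For cohort B, most recent systemic therapy and the duration of that therapy will be summarized within each of the following subgroups". The two subgroups are patients whose last therapy was adjuvant and patients whose last therapy was for locally advanced or metastatic disease. Three things are reported: treatment duration, time to progression, and how often each therapy was used.

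The two time variables have different origins. Duration runs from the start to the end of the therapy, plus 1. Time to progression is given as "median time to progression (date of progression – date of first dose + 1" (the bracket closes after the 1).

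SAP 6.1.2 defines the date of first dose as "the date of the first dose of study drug or NSAID/fulvestrant". In the same list, study drug "refers to abemaciclib or placebo" and study treatment "refers to study drug plus NSAID/fulvestrant". These are the treatments given in this trial. No section gives the term another meaning for therapies received before it.

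Protocol 7.1, Criterion 2b, sets out four routes into Cohort B. In each, relapse or progression has already happened. One example is "relapsed with radiologic evidence of progression within 1 year from completion of adjuvant letrozole or anastrozole".

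**The concern.** The formula describes the patient's history before the trial, but its origin is a defined term for an event inside the trial. Under Criterion 2b the progression comes first and the first study dose later, so the subtraction runs backwards. The result measures the gap between relapse and starting study treatment, with its sign reversed. It does not measure how long the prior therapy held the disease.

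At stake is one line of a baseline table that helps a reader see how quickly Cohort B patients had progressed on their last therapy. A programmer who follows the definitions would fill it with numbers that say nothing about that. A second programmer who guesses the intent would produce different numbers from the same SAP.

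**Working it through.** **Inputs.**
- Formula as written: SAP 6.4.4, P − F + 1, where P is the progression date and F is the date of first dose.
- Meaning of F: SAP 6.1.2, first dose of on-study treatment.
- Order of dates: Protocol 7.1, Criterion 2b, puts P before enrolment. Under SAP 5.3, first dose follows randomization, by no more than 7 days. So P falls before F.
- Comparison formula: P − S + 1, where S is the start of the prior therapy, as in the duration formula of the same sentence.
- The documents contain no patient-level dates. All dates and intervals in the table below are assumptions for illustration.

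**The SAP's own date arithmetic.** SAP 6.1.2 works two study-day examples with first dose on 06JUN2014. An event on 08JUN2014 gives 8 − 6 + 1 = 3. An event on 05JUN2014 gives 5 − 6 = −1, with no 1 added because the event precedes first dose. Both match the SAP. By that convention, an unconditional + 1 suits an origin that comes before the event, which hints that S was meant in 6.4.4.

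**General result.** If progression is g days before first study dose, P = F − g, and

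P − F + 1 = −g + 1 = −(g − 1).

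S does not appear, so the value cannot depend on time on the prior therapy.

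| Assumed history | Interval S to P (days) | g (days) | As written, −(g − 1) | From start of therapy, P − S + 1 |
|---|---|---|---|---|
| First-line from 1 Sep 2017, progression 10 Jan 2018, first study dose 5 Feb 2018 | 131 | 26 | −25 | 132 |
| Adjuvant from 1 Jan 2013, progression 1 Mar 2017, first study dose 10 Apr 2017 | 1520 | 40 | −39 | 1521 |
| 6 months first-line | 182 | 14 | −13 | 183 |
| 24 months adjuvant | 730 | 28 | −27 | 731 |
| 12 months | 365 | 60 | −59 | 366 |
| 12 months | 365 | 1 | 0 | 366 |

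The last two rows have the same prior history and get −59 and 0. The first two differ more than elevenfold in time to progression (1521/132 = 11.5) and get −39 and −25.

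**Edge cases.** Progression dated the day before first dose gives 0, not a negative number. SAP 6.4.4 sets a missing day to the 15th. If progression is known only as June 2014 and first dose was 06JUN2014, the formula gives 15 − 6 + 1 = +10. Neither value is a time on prior therapy.

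**The case against.** The best reply is that the section supplies the meaning. The heading is about prior therapies, and the other terms in the sentence (start, end, progression) are unqualified and plainly refer to the prior therapy. Read the same way, first dose means the first dose of that therapy, and the formula is right. A negative median would also be noticed in any output. This shows what was intended, and the error is most likely one of wording. It does not make the text correct. The SAP defines this term, and the same sentence uses a different term for the start of the prior therapy, so a reader has grounds to think a different date is meant. Some patients' prior therapy was itself an NSAI, but that does not bring it under the definition: SAP 6.1.2 pairs the NSAI or fulvestrant with study drug as study treatment.

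Three stronger readings are tempting, and the documents support none of them.

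- **The summary tells nothing about resistance.** Treatment duration in the same sentence is correctly defined and approximates time to progression for patients who progressed while on therapy. It is not a full substitute, since Criterion 2b also admits relapse up to 1 year after completing adjuvant letrozole or anastrozole.
- **The resistance stratum is left unchecked or wrong.** No section uses this table to derive or verify it. SAP 6.7 takes the factor from the eCRF and cross-tabulates it with the IWRS value, and SAP 6.4.2 summarises it separately. Even the corrected time could not settle the category alone: the metastatic limb of primary resistance is "progression within first 6 months of initiating first-line endocrine therapy while on endocrine therapy", so being on therapy matters too, and a group median cannot classify individuals.
- **The key secondary PFS result is affected.** PFS runs from randomization under its own rules, and SAP 6.7.2.1 spends no alpha on Cohort B and treats its tests as descriptive.

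**Conclusion.** The point holds as a wrong origin in one derivation. As written, time to progression on the most recent prior therapy in Cohort B would generally be at or below zero, equal to −(g − 1) days and independent of time on that therapy. Imputation to the 15th can occasionally give a small positive value. It could touch most of the roughly 150 planned Cohort B patients, but only in one descriptive baseline summary. PFS, alpha, power, sample size and the stratification factor are unaffected.

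The conclusion rests on taking the SAP's defined term at its word and on Criterion 2b placing progression before enrolment. The individual day counts rest on assumed dates; the general formula does not. The severity is low, and the reason to act is that the correction is almost free.

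**What to change.** In SAP 6.4.4, replace the date of first dose in the time-to-progression formula with the date of start of the most recent systemic therapy. The formula becomes progression date minus that start date, plus 1, which matches the duration formula beside it. The existing rule for partial dates can stay.

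The cost is a few words. The start date is already needed for duration and the progression date is already in the formula, so no new data are collected. Protocol 12.2.1 lets minor clarifications of this kind be made in the SAP before the sponsor unblinds the aggregate database. After that, the change and its reason go in the clinical study report. Reporting the result by resistance stratum would be an optional extra and is not needed for the correction.

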### **6.4.5. Post Study Treatment Discontinuation Therapies**

Therapies received following study treatment discontinuation will be summarized by arm. Therapies will be summarized overall and by category: endocrine therapy or targeted/chemotherapy.

## 6.5. Treatment Compliance

Treatment compliance of abemaciclib/placebo will be measured by pill counts and summarized. Compliance will be calculated as the ratio of total dose taken to the total assigned dose (minus any dose adjustments and doses omitted/withheld for medical or logistical reasons). The total assigned dose for a patient with no adjustments, omissions, or extensions for logistical reasons is  $150 \text{ mg per dose} \times 2 \text{ doses per day} \times 28 \text{ days} = 8400 \text{ mg}$ .

For cohort A, treatment compliance of NSAID will be measured based on pill count data, and will be summarized. Compliance will be calculated as the ratio of the number of doses taken to the total number of assigned doses (minus any dose adjustments and doses omitted/withheld for medical or logistical reasons). The total assigned dose for a patient with no adjustments, omissions, or extensions due to logistical reasons is  $1 \text{ dose per day} \times 28 \text{ days} = 28 \text{ doses}$ .

For cohort B, fulvestrant is administered in the clinic.

## 6.6. Concomitant Therapy

All medications will be coded to the generic preferred name according to the current World Health Organization (WHO) drug dictionary. All concomitant medications will be summarized for the ITT population using the preferred name.

## 6.7. Efficacy Analyses

For cohort A, the stratification factors for the analysis of primary and secondary analyses are:

- nature of disease (visceral metastases vs non-visceral metastases)
- prior (neo)adjuvant endocrine therapy (prior therapy with disease-free interval  $>12$  months from completion of treatment vs. prior therapy with disease-free interval  $\leq 12$  months from completion of treatment vs. no prior therapy).

For cohort B, the stratification factors for the analysis of primary and secondary analyses are:

- nature of disease (visceral metastases versus non-visceral metastases)
- sensitivity to endocrine therapy (primary resistance versus secondary resistance).

The stratification factors are captured in the IWRS and on eCRFs. Unless otherwise specified, all stratified analyses will be based on the stratification factors per eCRF. A cross tabulation of the frequency of each level of each stratification factor per IWRS and eCRF will be produced.

### 6.7.1. Primary Endpoint: Progression Free Survival of Cohort A

#### 6.7.1.1. Definition

The primary efficacy measure is progression-free survival of cohort A as defined by RECIST Version 1.1 and determined by the investigator. The PFS time is measured from the date of randomization to the date of objective progression or the date of death due to any cause, whichever is earlier.

If a patient is not known to have progressed or died at the time of analysis, PFS time will be censored at the last known progression-free assessment. The detailed censoring rules are described in the table below (Table JPBQ.6.1).

**Table JPBQ.6.1. Rules for Determining Date of Progression or Censor for Progression-Free Survival**

Rule	Situation	Date of Progression or Censor	Outcome
1	No baseline tumor assessments	Date of Randomization	Censored
2	No post baseline assessments and no death	Date of Randomization	Censored
3	No documented progression and no death (with a post-baseline tumor assessment)	Date of last adequate tumor assessment	Censored
4	Patient lost to follow-up (or withdrew consent from study participation) before documented progression or death	Date of last adequate tumor assessment	Censored
5	Documented progression	Date of documented progression. If a tumor assessment was done on multiple days, use the earliest date for that visit.	Progressed
6	Death without documented progression	Date of death	Progressed
7	Documented progression or death after missing $\geq 2$ consecutive post-baseline tumor assessments	Date of last adequate tumor assessment before missed assessments or date of randomization, whichever is later	Censored

Note: Progression-free survival and associated outcome is determined by the earliest of the dates above, if more than 1 situation applies.

### 6.7.1.2. Hypotheses and Analysis

Letting  $S_A(t)$  and  $S_P(t)$  denote the progression free survival functions of Abemaciclib + NSAI and placebo + NSAI respectively, the null hypothesis

$$H_0: S_A(t) = S_P(t)$$

will be tested against the one sided alternative hypothesis

$$H_1: S_A(t) > S_P(t).$$

There is 1 planned interim analysis and 1 primary analysis to test these hypotheses. At each analysis, the hypotheses above will be tested using a one sided stratified log rank test, stratified by nature of disease and prior (neo)adjuvant endocrine therapy.

The interim analysis is planned to take place after approximately 119 (70%) investigator assessed PFS events have occurred. The cumulative 1-sided type I error rate of .025 will be maintained using the O'Brien Fleming boundary.

Therefore, if the interim analysis is performed after exactly 119 events have been observed, a 1-sided p-value of less than 0.0082 (corresponding approximately to an observed hazard ratio <0.627 under an exponential model) will need to be observed to declare statistical significance (see Table JPBQ.6.2).

